4.4 Protocol Deviations

Protocol deviations and eligibility deviations will also be summarized by treatment group. Protocol deviations will be reviewed on a case-by-case basis and assessed if they are considered major deviations for this study. The final list will be compiled before database lock. Examples of major protocol deviations may include, but are not limited to, the following:

- Deviation from inclusion/exclusion criteria that may affect efficacy endpoints
- Major study drug dosing errors or dose modifications that are not within the protocol specifications that may compromise subject safety or efficacy assessments.
- Administration of prohibited concomitant medication during the course of the study treatment period
- Any other deviation that impacts subject safety

4.5 Pre-study and Concomitant Therapy

Concomitant medications, other than study treatment, and medications taken prior to starting study treatment will be summarized for all subjects using the Safety population analysis set by treatment group. Concomitant medications will be recorded at each monthly clinic visit. Subjects are recommended to take calcium 1000 mg/day and vitamin D (cholecalciferol) 800 IU/day in

divided doses. Phosphodiesterase inhibitors such as sildenafil used to treat erectile dysfunction may be initiated or continued as per individual investigator discretion. Breast irradiation and/or tamoxifen to prevent and/or treat painful gynecomastia will also be permitted per individual investigator discretion. Subjects who require the initiation of bisphosphonate or other bone-targeted therapy (eg, those sustaining an osteoporotic fracture) while on study will be permitted to do so and remain on study, but subjects who have used a bone-modifying agent within 3 months prior to randomization will be excluded.

4.6 Prohibited Medications

No concomitant use of any anti-cancer therapy will be permitted. This will include surgery, radiation therapy, and other secondary hormonal therapies including first generation antiandrogens, 5-alpha reductase inhibitors (i.e. finasteride, dutasteride), megestrol acetate, immunotherapy, chemotherapy, or other investigational agents while on study. Start of any of these therapies will result in discontinuation from the study. Nutritional supplements containing saw palmetto or pomegranate are also specifically prohibited.

As a class effect, androgen receptor antagonists have been associated with seizures due to an off-target mechanism of action (GABA_A inhibition). To date, no subjects receiving apalutamide have experienced seizures, however, in preclinical experiments, at very high doses, dogs treated with apalutamide had tremors and generalized seizures. Subjects will be closely monitored for seizures, but as a precautionary measure, the following drugs known to decrease the seizure threshold or cause seizure will be prohibited.

- Aminophylline, theophylline
- Atypical anti-psychotic drugs: clozapine, olanzapine, ziprasidone, bupropion
- Phenothiazine anti-psychotic drugs: chlorpromazine, mesoridazine, thioridazine
- Tricyclic and tetracyclic anti-depressants: amitriptyline, desipramine, doxipine, imipramine, maprotiline, mirtazapine (Remeron)
- Lithium
- Meperidine (Demerol) and pethidine

4.7 Reasons for Study Discontinuation

Subjects will discontinue study protocol treatment for the following reasons, whichever comes soonest:

- PSA progression
- Radiographic progression, defined as the detection of new metastasis on either bone scan or cross-sectional imaging (CT or MRI).
- Subject or treating physician decision
- Unacceptable toxicity
- Non-protocol therapy

5. EFFICACY

This section outlines the planned analyses of the primary, secondary, and other efficacy endpoints of the study.

Efficacy analyses will be performed in the ITT population, incorporating the randomization stratification factors. All continuous variables will be summarized using number of subjects (n), mean, standard deviation (SD), median, minimum, and maximum. Categorical variables will be summarized with count and percentage.

Time-to-event endpoints will be summarized using the Kaplan-Meier method [6] and displayed graphically where appropriate. Median event times and two-sided 95% confidence interval (CI) for each treatment group will be provided. Stratified Cox proportional-hazard models will be used to estimate the hazard ratio (HR) and its 95% CI. The stratification factors to be used in the analysis are PSADT (< 6 months vs. 6-12 months), and age at study entry (≤ 70 years vs. > 70 years).

The testing for the time-to-event endpoints will be based on the stratified log rank test; non-stratified log rank test will be performed as a sensitivity analysis, as appropriate. Multivariate Cox regression analysis, adjusting for important selected prognostic factors.

The proportional hazard assumption will be assessed graphically by plotting log (-log [estimated survival distribution function]) against log (survival time). The resulting graphs should have approximately parallel lines when the assumption holds. If the proportional hazards assumption is reasonably met, then the HR will be used as an estimate of treatment effect. If the proportional hazards assumption is violated, then the inference remains statistically valid for testing equality in survival distributions, but treatment effect will only be estimated using the median time to event in each treatment group.

Endpoints with binary outcome will be summarized by descriptive statistics (count and percentage) by the treatment group. The risk ratio or risk difference (treatment: control) will be reported along with the corresponding two-sided 95% CI. The two treatment groups will be compared by using the chi-square test; Fisher's exact test may be used if the expected counts in some of the cells are less than 5.

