The PSA working group has suggested that duration of clinical activity is a key intermediate endpoint in initial Phase 2 trials of agents conducted in the BCR disease population [50]. Indeed, in an exploratory analysis of a trial of IADT in BCR patients, Yu and colleagues demonstrated that in patients who completed the first cycle of IADT, a shorter duration of the first “off treatment” interval was associated with a shorter time to developing castrate resistant prostate cancer and shorter overall survival [53]. In the proposed trial, the time to PSA progression from the initiation of protocol therapy (ie, Day 1 of On-therapy Period) will be evaluated for each of the 3 treatment arms. This analysis is exploratory in nature, both because the definition of “PSA progression” and the consequent resumption of therapy on an intermittent program is arbitrary, and because this endpoint requires a sufficient number of patients and duration of follow-up to record enough PSA progression events to have adequate statistical power to detect a difference between study arms. Nevertheless, data suggesting that the time to PSA progression was similar with ARN-509 monotherapy or with LHRHa monotherapy, or alternatively, suggesting a longer time to PSA progression when ARN-509 was added to LHRHa monotherapy would be provocative, and serve as the potential basis for launching a more definitive Phase 3 trial.

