5.3 Secondary Endpoints

The following secondary endpoints will be analyzed:

A) Quality of Life:

- Mean change from baseline in total FACT-P score over time
- Mean change from baseline in EORTC QLQ-C30/PR25 score over time
- Mean change from baseline in SHIM score over time

B) PSA Modulation:

- Time to PSA progression, which is defined as a rise to greater than 50% of the baseline serum PSA or rise of 2 ng/mL or more above the nadir, whichever is higher, confirmed by repeat measurement at least 2 weeks later (see Table 1 for the censoring rules).
- Proportion of subjects without evidence of PSA or radiographic progression during the 24-month treatment period and with recovery of serum testosterone at 24 months. Testosterone recovery will be defined as a serum testosterone greater than 150 ng/dL.
- Proportion of subjects with a PSA less than 0.2 ng/mL after 7 months of protocol therapy

C) *Metabolic and Hormonal*

- Mean change from baseline in markers of insulin resistance (including body mass index, fasting glucose/insulin, and hemoglobin A1C), fasting lipid profile, and bone mineral density as measured at the femoral neck, and lumbar spine by DEXA scan over time
- Time to testosterone recovery to greater than 50 ng/dL (non-castrate) and greater than 150 ng/dL during the off-therapy observation period for subjects randomized to the LHRHa-based treatment arms (see Table 1 for the censoring rules)
- The mean change from baseline in serum DHT and estradiol levels over time

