5.3.1.2 PSA Modulation

The proportion of subjects without PSA or radiographic progression and who have recovered serum testosterone to greater than 150 ng/dL at 24 months from Day 1 will be compared for subjects treated apalutamide monotherapy vs. LHRHa monotherapy and for apalutamide + LHRHa vs. LHRHa monotherapy. The proportions by treatment will be compared using the chi-square test or Fisher's exact test as appropriate and summarized using either risk ratio or risk difference and corresponding 95% confidence interval. Results will be summarized at 24 months from Day 1 with 95% confidence intervals for each treatment arm. Subjects who withdraw from the study prior to 24 months after Day 1 will not be included and this analysis will be conducted as modified intent-to-treat (mITT).

The proportion of subjects with a PSA less than 0.2 ng/mL after 7 months of protocol therapy will be analyzed using similar approaches for proportion of subjects without evidence of PSA or radiographic progression during the 24-month treatment period and with recovery of serum testosterone at 24 months.

The probability distributions by treatment group of the time to PSA progression will be estimated using the Kaplan-Meier method. Durations will be measured from Day 1 of study treatment to the first date of PSA progression. The log-rank test will be used to compare the distribution of time to PSA progression.

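### If proportional hazards is judged violated, the SAP leaves time to PSA progression with a log-rank p-value and separate arm medians, but no between-arm effect estimate with a confidence interval

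*SAP*

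**What the plan says.** SAP section 5 plans Kaplan-Meier curves, a stratified log-rank test and a stratified Cox model for time-to-event endpoints. By arm, "Median event times and two-sided 95% confidence interval (CI) for each treatment group will be provided". Proportional hazards is judged by eye from a log-minus-log plot, whose lines should be roughly parallel. "If the proportional hazards assumption is reasonably met, then the HR will be used as an estimate of treatment effect". If it is not met, the test is kept for inference, but "treatment effect will only be estimated using the median time to event in each treatment group".

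For this endpoint, SAP 5.3.1.2 and Protocol 11.4.2 add only Kaplan-Meier estimation and a test: "The log-rank test will be used to compare the distribution of time to PSA progression". The event, in SAP 5.3, is "a rise to greater than 50% of the baseline serum PSA or rise of 2 ng/mL or more above the nadir, whichever is higher", with confirmation. On the clock, SAP 5.3.1.2 says "Durations will be measured from Day 1 of study treatment to the first date of PSA progression". Neither document states an expected event count, hazard, median or power for this endpoint. Protocol 6.4.2.3 calls the analysis exploratory and warns that "this endpoint requires a sufficient number of patients and duration of follow-up to record enough PSA progression events" with adequate power.

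**The concern.** A median in each arm describes the arms one at a time. It does not give the size of the difference or its uncertainty. Once the plot is read as a violation, the hazard ratio is no longer the effect estimate, and no difference or ratio of medians, restricted mean, fixed-time difference or piecewise hazard ratio takes its place.

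This matters because Protocol 6.4.2.3 says that a similar time to PSA progression with monotherapy, or a longer one with the combination, could help justify a Phase 3 trial. A non-significant log-rank test in 30 men per arm cannot support similarity; that needs an estimate with an interval. Because violation has no numerical criterion, the reader also cannot tell in advance which effect measure will be reported.

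**Working it through.** **Plan's own figure.** There is none for this endpoint. The 30 men per arm were set by FACT-P. That calculation (27 evaluable per arm, 7.5 points, SD 8.7, two-sided 0.025) reproduces at 80.2% power against the stated 80%, but says nothing about PSA events.

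**Step 1: what remains if proportional hazards is judged violated.**
- Log-rank test: kept; a p-value.
- Hazard ratio: no longer the effect estimate.
- Median with 95% CI in each arm: kept.
- Any contrast between arms with a CI: none specified.

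This step needs no assumption about event rates.

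**Step 2: is violation plausible?** Inputs from the documents:
- 12 months on therapy, then 12 months off, with one clock from Day 1.
- AR-antagonist monotherapy does not lower testosterone to a castrate level (Protocol 1.3.3).
- Median recovery after ADT (Protocol 6.4.2.3): 12.9 and 16.6 weeks in one report (12.9 × 7 / 30.4 = 3.0 months; 16.6 × 7 / 30.4 = 3.8 months), and about 10 months in another that used a threshold of 288 ng/dL.

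Assumptions: hazard 0.004 per month on therapy and 0.04 to 0.08 per month once off-therapy risk begins. That risk begins at Month 12 for monotherapy and after a lag for LHRHa. Cumulative hazard to Month 18, with 0.08 and a 4-month lag:
- monotherapy: 12 × 0.004 + 6 × 0.08 = 0.528
- LHRHa: 16 × 0.004 + 2 × 0.08 = 0.224
- ratio: 0.528 / 0.224 = 2.4

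With 0.04 the ratio is (0.048 + 0.24) / (0.064 + 0.08) = 2.0. After Month 18 the two hazards are equal. Simulated Cox hazard ratios agree:

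| Lag for LHRHa | To Month 18 | After Month 18 | Single Cox HR |
|---|---|---|---|
| none (0.08) | 1.0 | 1.0 | 1.0 |
| 4 months (0.04 to 0.08) | 2.1 to 2.5 | about 1.0 | 1.2 to 1.4 |
| 10 months (0.08) | about 6.5 | 1.5 to 1.8 | 2.2 to 2.8 |

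The departure comes from the difference in lag. In combination against LHRHa both arms are castrate on therapy and both must recover, so this mechanism is weaker there.

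**Step 3: would medians be reached?** Follow-up does not stop at Month 24. PSA continues every 3 months (Protocol 7.7), and men without progression are censored at their last PSA (SAP Table 1). The protocol abstract gives two timelines: a 36-month cutoff with 12 months' accrual (36 − 12 = 24, so 24 to 36 months per man), and last consent at 4 years with the cutoff 24 months later (24 to 24 + 48 = 72 months). Chance that an arm of 30 does not reach its median, with 0 to 10% yearly loss and assumed progression by Month 24:

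| Progressed by Month 24 | 24 to 36 months | 24 to 72 months |
|---|---|---|
| 25% | 85 to 86% | 10 to 16% |
| 35% | 48 to 50% | 2% or less |
| 45% | 12 to 17% | about 0 |
| 50% | 6 to 9% | about 0 |
| 60% | under 1% | about 0 |

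A second model takes 12 months, plus a lognormal recovery delay (log SD 0.4), plus an exponential time with median 8 months. With 24 to 36 months' follow-up and no loss, the LHRHa median is reached in 99% of trials for a median delay of 5 months and 91% for 8 months. With 24 to 72 months it is reached in about 100%.

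**Step 4: precision of a replacement, 30 per arm.**
- Difference in Kaplan-Meier proportion at 24 months, no earlier censoring: SE = √(2p(1−p)/30). For p = 0.5, √(0.5/30) = 0.129 and the half-width is 1.96 × 0.129 = 0.253. For p = 0.3 or 0.7, √(0.42/30) = 0.118 and the half-width is 0.232.
- Restricted mean difference to 24 months: simulated SE about 1.2 to 1.4 months, so half-widths of about 2.3 to 2.7 months.

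**The case against.** The best defence is that little is lost. The endpoint is secondary and openly exploratory. The curves, the test and both medians with intervals are still reported, and a reader can compare medians informally. SAP 5.3.1.2 also plans a Month 24 proportion with a risk ratio or difference and a 95% CI. With few events, a log-minus-log plot may not show a clear violation, and the hazard ratio would then stay in use.

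Most of this stands and limits the weight of the point. It does not close the gap. Informal comparison of two medians has no stated uncertainty. The Month 24 proportion is a composite that also requires testosterone recovery and no radiographic progression, and it excludes men who withdrew, so it does not isolate PSA progression.

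A reader might go further and infer that the design makes medians inestimable. That follows only if every man is censored at Month 24. The chance of at least 15 progressions among 30 is then 57%, 18% and 2% for true risks of 50%, 40% and 30%. The documents continue PSA follow-up beyond Month 24, and longer-followed men extend the curve of the whole arm. A reader might also infer that this endpoint is the main anti-cancer signal for both hypotheses. Hypothesis 1 speaks of comparable PSA suppression, and Hypothesis 2 lists time to PSA progression among several findings.

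**Conclusion.** The gap is real and rests on the SAP's wording alone: under judged non-proportionality, time to PSA progression has no planned between-arm estimate with a CI, whether or not the medians are reached. That the rule would be triggered is a reasonable inference for monotherapy against LHRHa. It rests on a difference in lag guided by the cited recovery times and on assumed hazards. It is not shown for combination against LHRHa, and no probability of failing the visual check can be derived from the documents.

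Unreached medians are a conditional risk. They matter under the 36-month cutoff if clearly fewer than half the men progress by Month 24, and are unlikely with 24 to 72 months' follow-up. The documents give no event rate to decide between these cases. The primary FACT-P analysis is unaffected. This is a cheap improvement with modest impact.

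**What to change.** In SAP section 5, replace the sentence that confines estimation to medians with: report the between-arm difference in Kaplan-Meier PSA-progression-free proportion at 24 months and the difference in restricted mean time to 24 months, each with a 95% CI, for each of the two comparisons, together with arm medians and 95% CIs where reached.

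Two details should be settled with it. State which day counts as Month 24, since visits have a ±7-day window. The sentence being replaced also governs time to testosterone recovery, so either limit the new text to PSA progression or give that endpoint its own time point. Reporting these measures whatever the plot shows would also remove the dependence on a visual judgement.

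The cost is one SAP sentence and a few lines of output; the curves are already planned and no new data are needed. The drawbacks are the wide intervals shown above and that measures stopping at 24 months ignore later follow-up, which the log-rank test still uses. The change should be made before comparative results for this endpoint are examined.

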5.1 Analysis Specification

5.1.1 Level of Significance

In general, a two-sided significance level of $\alpha = 0.05$ will be used for all hypothesis testing and all CIs will be calculated on the two-sided 95% confidence level, unless otherwise specified. Since this is a three-arm study testing two simultaneous hypotheses, $\alpha/2 = 0.025$ level of significance will be used to test each.

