1.4 Sample Size Justification

The expected mean decline in FACT-P score and within group standard deviation for the control arm treated with 12 months of LHRHa monotherapy are 4-8 and 8-12 points, respectively, based on prior studies of measuring QOL using FACT-P among men treated with ADT [1, 2, 3]. A change in total FACT-P score that is clinically meaningful and impacts treatment in prior studies ranges from 5-8 points depending on cancer subtype [4]. Approximately 30 subjects will be randomized to each of the 3 treatment arms for this comparison. Accounting for a dropout/questionnaire non-completion rate of 10%, this will allow for 27 evaluable subjects per study arm. For the comparison of the mean change in FACT-P score between apalutamide monotherapy and LHRHa monotherapy, this sample size has 80% power to detect an effect size of at least 0.86, corresponding to a difference of 7.5 points in mean 12 month change in FACT-P

score between treatment groups with a common standard deviation for the change in each arm of 8.7 which is similar to the reported standard deviation for LHRHa monotherapy. This is based upon a 2-group t test, using a bi-directional level of significance of 0.025 (adjusted for 2 comparisons). To test for non-inferiority in QOL with apalutamide + LHRHa compared with LHRHa monotherapy, inferior QOL is defined as a greater than 7-point difference in mean change in FACT-P score between the treatment groups and the common standard deviation is again assumed to be 8.7. This sample size has 82% power to reject the null hypothesis of a difference in mean score and accept the alternative hypothesis of non-inferiority with an effect size of at least 0.81, using a 2-group t-test with 2-sided α of 0.025.

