5.2.1 Analytic Plan for the Primary Endpoint

Change from baseline in FACT-P total scale will be analyzed using a mixed-model for repeated measures. The model will include baseline scale, treatment, month (categorical), and treatment-by-month interaction as covariates. An unstructured variance-covariance matrix will be used to model within-subject errors, but simpler structures (eg, compound symmetry) may be used to ensure estimation convergence. Change from baseline will be estimated using least-squares means with factor levels weighted according to overall baseline sample means. Data up to 12 months will be included in the analysis and the primary time point of interest will be at 12 months. Contrasts will be set up to compare apalutamide monotherapy vs. LHRHa monotherapy and apalutamide + LHRHa vs. LHRHa monotherapy. To test for non-inferiority with respect to apalutamide + LHRHa compared with LHRHa monotherapy, inferior boundary is defined as a greater than 7-point difference in mean change in FACT-P total score. The estimated least-squares mean (+/- SE) over time will be presented using a line plot. A sensitivity analysis will be conducted by including data up to 24 months.

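### The SAP's default 95% confidence interval does not match the two-sided 0.025 superiority test, so a reported FACT-P interval can exclude zero when that test fails

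*SAP*

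**What the plan says.** SAP 5.1.1 opens with a general rule: two-sided 0.05 for testing, and "all CIs will be calculated on the two-sided 95% confidence level, unless otherwise specified". It then makes an exception for the primary analysis. "Since this is a three-arm study testing two simultaneous hypotheses", half of alpha, the 0.025 "level of significance will be used to test each". That exception changes the test level and does not mention intervals.

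SAP 1.4 agrees with the split. The superiority comparison is sized "using a bi-directional level of significance of 0.025 (adjusted for 2 comparisons"), and non-inferiority is sized "using a 2-group t-test with 2-sided α of 0.025". Protocol 11.1 gives the same levels.

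SAP 5.2.1 sets out the primary analysis: "Contrasts will be set up to compare apalutamide monotherapy vs. LHRHa monotherapy", and likewise for the combination, with a 7-point inferiority boundary. It names no confidence level for either contrast. The only measure of uncertainty it mentions is a standard error around the least-squares means on a line plot. Protocol 11.4.1 is the same in these respects. Where the SAP does name an interval level elsewhere (the opening of section 5 and section 5.3.1.2, for time-to-event and binary endpoints), the level is 95%. SAP 5.3.1.3 says that secondary endpoints are not adjusted for multiplicity.

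**The concern.** A two-sided test at 0.025 corresponds to a 97.5% interval. If the 95% default is applied to the superiority contrast, there is a band of results, those with p between 0.025 and 0.05, in which the interval excludes zero and the prespecified test does not reject. The plan has no rule for reading such a result.

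The band matters here because, under the planning values, it contains the lower end of the 5 to 8 points that the SAP regards as clinically meaningful. Protocol 1.6 also says that a favourable quality-of-life result is to justify larger trials. A reader who sees an interval clear of zero may take the superiority question as answered when the test says otherwise.

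**Working it through.** **Inputs.** From SAP 1.4: 27 evaluable subjects per arm, SD of the 12-month change 8.7, superiority difference 7.5 points, non-inferiority margin 7 points, two-sided 0.025 for each test. From SAP 5.1.1: default interval level 95%. From Protocol 6.2.1: LHRHa monotherapy is the shared control. Allocation is 1:1:1.

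**1. Reproduce the plan's power.** The standard error of a contrast is 8.7 × √(2/27) = 2.368. The effect size is 7.5/8.7 = 0.86. With a two-group t test on 27 + 27 − 2 = 52 degrees of freedom, noncentral-t power at two-sided 0.025 is 80.2%. The SAP says that "this sample size has 80% power to detect an effect size of at least 0.86", so the model below is the plan's own.

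**2. Half-width of the interval against the threshold of the test.**
- 95% interval: 2.007 × 2.368 = 4.75 points.
- Two-sided 0.025 test, or 97.5% interval: 2.308 × 2.368 = 5.47 points.
- Ratio: 5.47/4.75 = 1.15.

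If the observed SD equals 8.7, differences between 4.75 and 5.47 points give conflicting messages. With a variance pooled over three arms (78 degrees of freedom) the band is 4.71 to 5.41.

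**3. How often the conflict occurs.** It is the power at 0.05 minus the power at 0.025, with the SD estimated from the data:

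| True difference | Power at 0.05 | Power at 0.025 | Conflict |
|---|---|---|---|
| 0 | 5.0% | 2.5% | 2.5% |
| 4 | 38.2% | 27.7% | 10.5% |
| 5 | 54.5% | 42.8% | 11.7% |
| 7.5 | 87.5% | 80.2% | 7.3% |

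At a true difference of zero the 2.5% divides equally between the two directions, so 1.25% favours monotherapy.

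**4. Joint coverage, for description.** With equal arms and a shared control, the covariance of the two contrasts is σ²/n and each variance is 2σ²/n, so the correlation is 0.5. The probability that both intervals cover is 90.9% at the 95% level (bivariate normal; 91.1% by simulation with 78 degrees of freedom) and 95.4% at the 97.5% level. Independent contrasts would give 0.95² = 90.25% and 0.975² = 95.06%.

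**5. Non-inferiority power.** For a true difference of zero, margin 7 and SD 8.7, noncentral-t power is 82.7% at one-sided 0.025 and 74.0% at two-sided 0.025. The SAP says "This sample size has 82% power to reject the null hypothesis", which agrees to within a point with the one-sided figure only. Using the SAP's stated effect size of 0.81 in place of 7/8.7 = 0.805 gives 83.2% and 74.6%, which does not change the conclusion. The literal alpha therefore points to a 97.5% interval for this contrast, and the stated power points to the bound of a 95% interval.

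**The case against.** The strongest reply is that the decision rule is the test. Each hypothesis is tested at 0.025, and the split controls the familywise error whatever interval is printed. This stands. A reader might infer that multiplicity control is lost, but that would need the 95% interval to decide superiority, and neither document says it does.

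Second, a reader might say that the plan fails to deliver 95% joint coverage. The coverage of about 91% is correct, but the documents use the split for testing two hypotheses and never set a coverage target. The figure describes the pair of intervals and is not a failure against the plan.

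Third, the SAP does not expressly promise a 95% interval for the FACT-P contrasts. The rule is a general default with an exception clause, and the error bars named for the primary analysis are standard errors. One could read the interval level as moving with the test level. The text does not say so, however. The exception clause is never used for these contrasts, so the default governs any interval that is reported.

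Fourth, unadjusted intervals beside adjusted tests can be legitimate, and a printed p-value would reveal the conflict. That is true if the intervals are labelled as unadjusted; the SAP contains no such label.

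Finally, requiring 97.5% for both contrasts would go too far, because the non-inferiority alpha is itself unsettled.

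**Conclusion.** The mismatch is real and limited to reporting. For the superiority contrast, the stated interval rule and the stated test level disagree. Under the planning values they conflict in 7.3% of trials at the design effect, 11.7% at a true 5 points and 2.5% when there is no difference. No test, estimate or decision rule for superiority is wrong, and the familywise error stays controlled.

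The point values rest on 27 evaluable per arm, SD 8.7 and a two-group t test. The standard error from the repeated-measures model will differ somewhat, which moves the band in points. The band in p-values, 0.025 to 0.05, stays where it is. The joint coverage of about 91% depends on the correlation of 0.5 and hardly on the SD. For non-inferiority, the right interval level cannot be fixed until the plan's alpha and its power agree.

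**What to change.** In SAP 5.1.1 and 5.2.1, state that:
- apalutamide monotherapy versus LHRHa will be reported with a two-sided 97.5% confidence interval, matching its 0.025 test;
- any 95% interval also shown for that contrast is unadjusted and descriptive;
- the interval for the combination versus LHRHa will have the level that matches the alpha actually used against the 7-point margin.

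Before writing the third statement, reconcile the two-sided 0.025 (74.0% power) with the stated 82%, which is reproduced only at one-sided 0.025 (82.7%). Keep 95% for the secondary endpoints.

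For superiority the change takes one sentence, and the interval becomes about 15% wider (half-width 5.47 instead of 4.75 points). The test, the data and the sample size do not change. The cost for non-inferiority depends on the reconciliation: if two-sided 0.025 is kept, the power to be stated is about 74%, not 82%.
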